7.7 Efficacy Analyses

All efficacy endpoints will be summarized within each disorder group (Dravet syndrome or CDKL5) and by treatment group.

Summary statistics for the total numbers of the following measurements per 28 days along with percent changes from Baseline per 28 days will be tabulated for the following:

- Convulsive/motor seizures
 - Tonic-Clonic Seizures
 - Hemiclonic Seizures
 - Drop Attacks
 - Tonic Seizures
 - Focal Motor Seizures
 - Staring seizures
 - Myoclonic seizures
- Use of rescue medications

- Emergency room visits/hospitalizations

For the primary endpoint, the percent change from baseline in 28 day convulsive seizure frequency in each treatment period, the method from Mary E. Putt and Vernon M. Chinchilli^[1] will be used. In short, differences d_{ij} between two treatment periods in percent change in total seizure frequency per 28 days will be calculated for each patient, where i is the sequence and j is the patient. Wilcoxon rank sum test and Hodges–Lehmann confidence interval will be applied to the two sequences d_{ij} , as in [1].

As a supportive analysis rank mixed models will also be used. The rank of percent change from baseline in 28 day total seizure frequency in each treatment period are used as dependent variables, with the rank of baseline 28 day total seizure frequency, treatment group, treatment sequence and treatment period as fixed factors, subjects within treatment sequence as random factors. The rank mixed model will be applied in each disorder group separately.

Summary statistics at each measurement time point, along with changes from Baseline will be tabulated for:

- Behavior Assessment System for Children
- VABS-II
- QOLCE

The same methods described above to assess efficacy outcome measures will be continued for subjects that enroll in the extension study up to Week 124 or final dose, if prematurely discontinued.

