1.5 Study Design

[figure not shown]
Crossover designs are usually statistically efficient and thus require fewer subjects. Additionally, the influence of confounding covariates is reduced because each crossover subject serves as his or her own control. A 12-week treatment period with ataluren provides sufficient time to assess changes in the subject's seizure activity and QOL while still allowing appropriate monitoring of the subject. Due to the lack of effective alternative treatment, subjects and their parents/legal guardians will be motivated to participate in this study. Therefore, we expect a low dropout rate.

The study to be conducted is a Phase 2 interventional study which includes the following: Screening (Week -4 to Week 0/Day 1), Treatment Period 1 (Week 0/Day 1 to Week 12), Washout Period (Week 12 to Week 16), crossover to Treatment Period 2 (Week 16 to Week 28), and a Follow-up visit after 4 weeks. Subjects who complete this study may be eligible to enroll in a 96-week open-label extension study (Week 28 to Week 124). A Follow-up visit is to occur 4 weeks after the last dose of study drug for all subjects, regardless of whether a subject discontinues prematurely or completes the End-of-Study (EOS) visit and/or the open-label extension. For subjects who enroll in the extension study, Follow-up is scheduled to occur at Week 128. The opportunity to enroll in the extension study will be explained to subjects during the initial study informed consent by the site investigator; subjects enrolling in the extension study do not need to re-consent.

The treatment period in this study ends at Week 124 (Visit 11). However, for subjects that want to continue on study medication beyond Week 124, PTC Therapeutics will continue to supply drug. All subsequent visits will be standard of care and any blood work will be at the discretion of the investigator. A follow up visit for subjects who do not want to continue will be scheduled 4 weeks following the last dose. Access to study drug will continue until commercial availability of ataluren for this indication or until a positive risk-benefit assessment in this indication is not demonstrated whichever is first.

The study design is shown in Figure 2. The Schedule of Events is provided in Table 1.

Figure 2: Study Design

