2 STUDY OBJECTIVES AND ENDPOINTS

2.1 Objectives

The primary objective of this study is to:

- Evaluate changes in convulsive and/or drop seizure frequency from Baseline following ataluren treatment in subjects with CDKL5 or Dravet syndrome resulting from a nonsense mutation.

The secondary objectives of this study are to:

- To determine changes in minor seizure types (absence, myoclonic, complex partial/focal dyscognitive) following ataluren treatment in subjects with CDKL5 or Dravet syndrome resulting from a nonsense mutation. (Seizure types as defined by the International League Against Epilepsy [ILAE] criteria [Appendix A].)
- Characterize the safety profile of ataluren in subjects with CDKL5 or Dravet syndrome resulting from a nonsense mutation

The exploratory objectives of this study are to:

- Evaluate changes from Baseline in cognitive, motor, and behavioral function as well as QOL following ataluren treatment in subjects with CDKL5 or Dravet syndrome resulting from a nonsense mutation.

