2.2.2 Secondary Endpoints

The secondary endpoints of this study are as follows:

- Changes in minor seizure types:
 - Number of myoclonic seizures
 - Number of staring (absence or complex partial) seizures
 - Number of other seizure types (atypical; absence, pure sensory seizure, etc)

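### No within-child ataluren-minus-placebo estimate is planned for the minor seizure types or for rescue-medication use

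*Combined protocol and SAP*

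**What the plan says.** The secondary efficacy objective in section 2.1 reads "To determine changes in minor seizure types (absence, myoclonic, complex partial/focal dyscognitive) following ataluren treatment". Section 2.2.2 lists three endpoints for it: "Number of myoclonic seizures", "Number of staring (absence or complex partial) seizures" and "Number of other seizure types (atypical; absence, pure sensory seizure, etc").

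Section 7.7 opens with "All efficacy endpoints will be summarized within each disorder group (Dravet syndrome or CDKL5) and by treatment group". It then tabulates 28-day totals and percent change from Baseline for a list that includes staring seizures, myoclonic seizures and rescue-medication use. Other seizure types are not in that list; only the opening sentence covers them.

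The crossover method is introduced with the words "For the primary endpoint, the percent change from baseline in 28 day convulsive seizure frequency in each treatment period". Each child's difference between the two periods is formed, and the two sequences are compared by a Wilcoxon rank-sum test with a Hodges-Lehmann interval. The same paragraph then calls the quantity total seizure frequency. The supportive rank mixed model, which has treatment, sequence, period and subject terms, is also for total seizure frequency.

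Section 1.5 supports the crossover design on the ground that "the influence of confounding covariates is reduced because each crossover subject serves as his or her own control".

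**The concern.** Every child is observed on both ataluren and placebo, so a direct within-child contrast is available for every diary endpoint. For the secondary efficacy objective the plan collects that contrast but does not report it.

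By-treatment means and SDs do not contain the within-child SD, so a reader cannot rebuild the contrast or its interval from the tables. Change from Baseline is a within-child measure. On ataluren alone, however, it does not separate a drug effect from placebo response, regression to the mean or time trend. Setting the two columns side by side gives a rough contrast, but one with no interval and no adjustment for period when the sequences are unequal.

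An effect on myoclonic or staring seizures that is consistent within children could therefore be hard to see. Adding the contrast after unmasking would make it post hoc.

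**Working it through.** **Which method covers which endpoint.** From sections 2.2.1, 2.2.2 and 7.7:

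- Convulsive seizures, or total seizures as the same paragraph of 7.7 later says: between-period difference, rank-sum test and Hodges-Lehmann interval.
- Total seizures: rank mixed model with period and subject terms.
- Myoclonic and staring seizures, and rescue-medication use: by-treatment summaries and percent change from Baseline.
- Other seizure types: covered only by the general sentence on by-treatment summaries.

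The last sentence of 7.7 carries the same methods forward, but into the open-label extension. It does not extend the crossover comparison to other endpoints. If total seizures include the minor types, those types enter a paired analysis only when pooled with the convulsive ones.

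**Inputs.** The plan states no power, alpha or standard error for these endpoints, so there is no figure to reproduce.

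- Mean 70 and SD 65 (section 7.4.1). These are for seizure frequency in general and are borrowed here for illustration.
- Meaningful difference 20% over placebo (section 7.4.1): 0.20 x 70 = 14.
- Randomized so far: 7 + 8 = 15 (section 7.1). Both groups are labelled Dravet there; one is presumably CDKL5.
- Within-child correlation rho is not given. The assumed range is 0.3 to 0.8.
- Sequence splits of 4/4 and 4/3 within disorder are assumed from the 1:1 allocation.

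**Precision.** From two column SDs alone, a reader can form only SE = SD x sqrt(2/n). The within-child contrast has SE = SD x sqrt(2(1-rho)/n) with balanced sequences. The ratio is sqrt(1-rho).

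| rho | ratio | n = 8: columns, within-child | n = 15: columns, within-child |
|---|---|---|---|
| 0.3 | 0.84 | 32.5, 27.2 | 23.7, 19.9 |
| 0.5 | 0.71 | 32.5, 23.0 | 23.7, 16.8 |
| 0.8 | 0.45 | 32.5, 14.5 | 23.7, 10.6 |

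**Power at the plan's own threshold.** The normal approximation is Phi(14/SE - 1.96), two-sided 0.05, with the within-child SE. For n = 8 it gives 7%, 9% and 16% at rho 0.3, 0.5 and 0.8. For n = 15 it gives 11%, 13% and 26%.

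**Period effect.** With 4 and 3 children per sequence, the plain column difference carries (4-3)/7 = 1/7 of any period shift. The comparison of between-period differences across sequences carries none.

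**Scale of the estimate.** In the ataluren-first sequence, Period 1 minus Period 2 equals the treatment effect plus the period shift. In the placebo-first sequence it equals minus the treatment effect plus the same shift. The difference between sequences is twice the treatment effect, so the Hodges-Lehmann shift must be halved.

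**What interval can be reached.** The smallest exact two-sided rank-sum p is 2/C(n1+n2, n1). For 4/3 it is 2/35 = 0.057, so the highest exact confidence level of a finite interval is 1 - 0.057 = 94.3%. For 4/4 it is 2/70 = 0.029, so a 95% interval can be reached. Ties, such as several children with no seizures of a type, make these levels approximate.

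**The case against.** Section 7.1 says the study was not powered for testing and offers an initial assessment of efficacy. With 7 or 8 children per disorder, keeping formal inference to the primary endpoint is defensible. The secondary objective asks for changes following ataluren, and change-from-Baseline tables address it as worded. The diaries are kept per child, so paired summaries could be produced later.

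Most of this stands, and it limits the point to a recommendation. It does not show that the contrast is planned anywhere. Lack of power is also a reason to use the pairing, because an estimate with an interval serves an initial assessment better than two separate columns.

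A reader might infer something stronger: that the plan analyses the ataluren and placebo columns as if they held different children. The documents do not support that. Section 7.7 specifies no unpaired test, no independent-groups interval and no independence assumption for these endpoints, and it tabulates change from Baseline, which is within child. Error rates or power of an unpaired test would therefore not describe this plan.

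Nor can it be said that the minor seizures stay outside every paired analysis, because total seizure frequency may include them. Section 2.2.1 also lists the effect on myoclonic seizures and rescue-medication use under the Primary Endpoint heading, so their status as secondary is not settled.

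**Conclusion.** The point holds as a gap in what is planned. None of the three minor seizure endpoints in 2.2.2, nor rescue-medication use, has its own ataluren-minus-placebo estimate or interval. That conclusion rests on the text and on no assumed number.

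The size of the gain depends on a correlation that the plan does not give: the SE falls to 0.84, 0.71 or 0.45 of the column-based value at rho 0.3, 0.5 or 0.8. The absolute SEs borrow an SD that is not specific to minor seizures. The gain is in estimation. At the 20% threshold, power stays at or below about 26% for 15 children over this range, so the added analysis should not be presented as a decisive test.

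**What to change.** Add to section 7.7, before unmasking:

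- For each minor seizure type in 2.2.2 (myoclonic, staring, other) and for rescue-medication use, compute each child's Period 1 minus Period 2 difference in the absolute 28-day rate. Section 3.1 requires only convulsive or drop seizures at entry, so a baseline count for these endpoints may be zero and percent change undefined.
- Compare the two sequences with the Hodges-Lehmann method already named for the primary endpoint, and halve the shift to give the ataluren-minus-placebo estimate.
- Report it by disorder group with an interval at its achieved exact confidence level (at most 94.3% for a 4/3 split), plus a combined estimate stratified by disorder.
- Label these results descriptive, with no multiplicity claim, and keep the by-treatment tables.
- Add other seizure types to the tabulation list, and reconcile 2.2.1 with 2.2.2 on the status of the myoclonic effect and rescue-medication use.

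The cost is a few lines of text and a few tables that reuse the primary-endpoint program. No new data or subjects are needed. The downside is a few extra unadjusted intervals.

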2.2 Endpoints

2.2.1 Primary Endpoint

The primary study endpoints of this study include:

- Change in convulsive and/or drop seizure frequency from baseline. Convulsive/Motor seizures to be counted are tonic-clonic seizures, hemiclonic seizures, atonic/drop attacks, tonic seizures, and focal motor seizures.
- The effect on myoclonic seizures (ie, persistence or disappearance) will also be evaluated.
- Data will be collected at Baseline and at each 6-week post-Baseline visit to identify changes in:
 - Number of episodes of status epilepticus, defined as a convulsion lasting > 10 minutes
 - Number of uses of rescue medications
 - Number of emergency room visits/hospitalizations

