3.1 Inclusion Criteria

Subjects who will be selected for this study must meet the following criteria:

1. Age \geq 2 years old and \leq 12 years old, male or female, at Week 0 (at time informed consent/assent is signed)
2. Documentation of a diagnosis of Dravet syndrome or CDKL5 deficiency resulting from a nonsense mutation in 1 allele, as evidenced by medical records, genetic testing, and the following clinical feature:
 - a. Failure to control seizures despite appropriate trial of 2 or more AEDs at therapeutic doses
3. Between 1 to 3 baseline AEDs at stable doses for a minimum of 4 weeks prior to enrollment (ie, Screening visit)
 - a. Vagus nerve stimulator (VNS), ketogenic diet, and modified Atkins diet do not count towards this limit but must be unchanged for 3 months prior to enrollment (Screening).
4. VNS must be on stable settings for a minimum of 3 months prior to the Baseline visit
5. If on ketogenic or modified Atkins diet, must be on stable ratio for a minimum of 3 months prior to the Baseline visit
6. Written consent obtained from the subject or subject's legal representative must be obtained prior to performing any study procedures
7. Minimum of 6 convulsive or drop seizures with duration $>$ 3 seconds over the 4 weeks of diary screening prior to randomization and \geq 6 convulsive or drop seizures with duration $>$ 3 seconds during the 4 weeks from Screening to Baseline.

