7.4 Efficacy Endpoint Definitions

7.4.1 Seizures

Based on observational studies of subjects with CDKL5 and Dravet syndrome in other drug studies, mean seizure frequency of 70 with a standard deviation of 65 has been estimated. From the epilepsy literature ([Cramer 1999](#)), a clinically meaningful difference will be a $\geq 20\%$ reduction in seizure frequency over placebo.

Seizure activity will be assessed based on ILAE criteria for the following:

- Motor seizure including tonic-clonic seizures, hemiconvulsive seizures, drop attacks, tonic seizures, focal motor seizures.
- Staring seizure is an absence seizure or a complex partial seizure.
- Myoclonic seizure is the persistence or disappearance seizure.
- Episode of status epilepticus: a convulsive state lasting longer than 10 minutes.

Baseline total number of seizures/emergency room visits/hospitalizations is defined as the total number of seizures/emergency room visits/hospitalizations during the 4-week Screening Period (Week -4 to Week 0 [Day 1]).

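### Percent change from Baseline is planned for outcomes with no minimum baseline and no rule for zeros; for rare ones such as emergency visits it may lose many subjects and bias the rest towards a fall

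*Combined protocol and SAP*

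**What the plan says.** Section 7.7 (Efficacy Analyses) asks for summary statistics of totals per 28 days, "along with percent changes from Baseline per 28 days will be tabulated for the following". The list covers convulsive/motor seizures, five single convulsive subtypes, staring seizures, myoclonic seizures, "Use of rescue medications" and "Emergency room visits/hospitalizations". Tables are by disorder group and treatment.

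Section 7.4.1 sets the baseline: it "is defined as the total number of seizures/emergency room visits/hospitalizations during the 4-week Screening Period". That definition does not name rescue use, but the Screening diary in Section 6.1.1.1 records it over the same four weeks.

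The only minimum is inclusion criterion 7 in Section 3.1, which requires at least 6 "convulsive or drop seizures with duration" above 3 seconds. It applies to the combined count. No section says what to do when a baseline is zero.

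Section 2.2.1 places rescue use and "Number of emergency room visits/hospitalizations" under the primary endpoint heading, and Section 2.2.2 makes myoclonic and staring seizures secondary endpoints. For the open-label phase, Section 7.7 adds: "The same methods described above to assess efficacy outcome measures will be continued for subjects that enroll in the extension study".

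**The concern.** Percent change divides by the baseline count, so it does not exist when that count is zero. As written, the columns for outcomes without a minimum cannot be produced unless the programmer chooses how to treat zeros, and that choice would be made with the data in hand.

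If such subjects are simply left out, two separate things can happen. The column may rest on very few children, because each table holds only about 7 or 8. And if the outcome is rare, those who remain are largely those who happened to have an event in the four-week window. Their later rate falls back towards its usual level, and this reads as improvement without any drug effect. Subjects who could only get worse are absent from that column.

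In the masked phase both treatments share the artefact, so it distorts each within-treatment figure more than the contrast between them. The extension has no placebo period to expose it.

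**Working it through.** **Inputs from the documents.** Baseline window 4 weeks (7.4.1). Treatment period 12 weeks, rescaled to 28 days (1.5.1, 7.7). Subjects randomized 7 + 8 = 15 (7.1). Combined convulsive/drop baseline at least 6 (3.1). The plan gives no zero-baseline share and no expected rate for any outcome without a minimum, so there is no figure of its own to reproduce. The event rates below are assumptions, shown as a range.

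**Common rate, no drug effect.** Let B be the 28-day baseline count, Poisson with mean m, and Y the later count per 28 days, also with mean m.

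- Share lost: P(B = 0) = exp(-m)
- Mean percent change among the rest: m × E[1/B | B ≥ 1] - 1

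| m per 28 days | Share lost | Expected evaluable of 15 | E[1/B given B ≥ 1] | Mean change |
|---|---|---|---|---|
| 0.2 | 82% | 2.7 | 0.951 | 0.2 × 0.951 - 1 = -81% |
| 0.5 | 61% | 5.9 | 0.879 | 0.5 × 0.879 - 1 = -56% |
| 1.0 | 37% | 9.5 | 0.767 | -23% |
| 1.5 | 22% | 11.7 | 0.666 | about 0% |
| 2.0 | 14% | 13.0 | 0.577 | +15% |
| 5.0 | 0.7% | 14.9 | 0.258 | +29% |

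Half the subjects are lost at m = ln 2 = 0.69, which is 0.69 × 365.25/28, or about 9 events per child-year. By disorder group (7 and 8 subjects), the expected number evaluable is 1.3 and 1.5 at m = 0.2, and 2.8 and 3.1 at m = 0.5. The mean change crosses zero at m = 1.50. The median crosses later: it is -17% at m = 1.5 and 0% at m = 2.

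**Persistent differences between subjects.** Let each child's rate follow a gamma distribution with mean m and shape k (smaller k means more variation). Then P(B = 0) = (k/(k + m))^k, and the mean percent change is [m/(k + m)] × (1 + k × E[1/B | B ≥ 1]) - 1.

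| m | Shape 2 | Shape 1 | Shape 0.5 | Shape 0.1 | Share lost |
|---|---|---|---|---|---|
| 0.2 | -74% | -68% | -59% | -28% | 83% to 90% |
| 0.5 | -46% | -40% | -31% | -12% | 64% to 84% |

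Variation shrinks the artefact but raises the share lost. At a mean of 2 the mean change lies between -1% and +6% over these shapes.

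**Seizure types a child either has or never has.** Suppose 30% to 40% of children have the type, at 2 to 14 per 28 days, and the others never do. Then 60% to 74% have a zero baseline, but the mean change among the rest is +8% to +29%. Subjects are lost and no spurious fall follows.

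**Combined convulsive count.** Section 7.4.1 gives a mean of 70 and SD of 65 without a time unit. Read as a 28-day negative binomial count, the chance of zero is 0.8% before the entry rule and nil after it. Given a baseline of at least 6, the mean change with no drug effect is about +2% and the median 0%.

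**The proposed statistic.** Y - B uses every subject and has expectation m - m = 0 with no drug effect. In simulation over all the gamma settings tried, its mean stayed within 0.003 of zero. Taking a ratio of totals among subjects with B ≥ 1 does not help: it still gives -44% at mean 0.5, shape 1.

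**The case against.** The strongest reply is that the affected columns are descriptive, in a study that Section 7.1 says was not powered for testing. The rank sum test with its Hodges–Lehmann interval and the rank mixed model use convulsive or total seizure frequency, which the entry rule keeps above zero. Raw totals per 28 days stand in the same tables, and both masked treatments carry the same artefact. All of this stands.

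A reader might infer that these baselines are usually zero, that most subjects will drop out, and that a large false fall will follow for every outcome listed. The documents do not support that. They give no rates for these outcomes, the mean fall vanishes near 1.5 events per 28 days and then reverses, and types that a child either has or never has lose subjects without a fall.

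A reader might also infer that new onset of an event goes unseen. It is absent from the percent column, but the raw totals show it, and Section 2.2.1 separately evaluates whether myoclonic seizures persist or disappear.

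Finally, removing percent change everywhere would have a cost. For frequent seizure types, one high-count child can dominate a mean absolute change among 7 or 8 subjects. That argues for a narrower remedy.

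The reply leaves one thing untouched: the stated statistic is undefined at zero, and the raw totals do not repair the column that reports it.

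**Conclusion.** The concern holds in a limited form. That percent change is planned for outcomes with no minimum baseline and no rule for zeros follows from the text and needs no assumption.

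The size is conditional. For rare outcomes, most plausibly emergency visits/hospitalizations and possibly rescue use, an assumed mean of 0.2 to 0.5 per 28 days gives 61% to 82% of subjects lost and a mean change of -56% to -81% under a common Poisson rate. With between-subject variation (gamma shape 2 to 0.1) the change is about -12% to -74%. At about 1.5 per 28 days or more the mean shows no material fall.

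The consequence is confined to descriptive percent-change columns. It matters most in the extension, where there is no comparator. Nothing here calls the primary or supportive test into question. The change is worth making because it is cheap, but the trial's main inference does not depend on it.

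**What to change.** In Section 7.7:

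- For emergency visits/hospitalizations and rescue use, replace percent change with absolute change in rate per 28 days on all subjects. In the masked phase only, add the within-subject ataluren-minus-placebo difference in rate; it cannot be formed in the extension.
- For single convulsive subtypes, staring and myoclonic seizures, add absolute change on all subjects, and print the number with a zero baseline beside any percent change.
- Keep percent change for the combined convulsive count.
- Show medians as well as means for absolute change.

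The cost is a sentence or two in Section 7.7 and revised columns in descriptive tables, with no new data. The downsides are small: rare outcomes leave the percent scale, and for high-count seizure types a mean absolute change can be driven by one child, which is why medians are needed.

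### Section 7.7 names convulsive seizure frequency as the primary variable but writes d_ij and the supportive rank model on total seizure frequency, whose seizure types are not stated

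*Combined protocol and SAP*

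**What the plan says.** Section 7.7 introduces the primary analysis as an analysis of "the percent change from baseline in 28 day convulsive seizure frequency in each treatment period" and refers to a published nonparametric crossover method. The next sentence abridges that method: differences d_ij "between two treatment periods in percent change in total seizure frequency per 28 days will be calculated for each patient". The Wilcoxon rank sum test and Hodges–Lehmann interval are then applied to the d_ij of the two sequences.

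For the supportive rank mixed model the same section says: "The rank of percent change from baseline in 28 day total seizure frequency in each treatment period are used as dependent variables". The model is fitted "with the rank of baseline 28 day total seizure frequency, treatment group, treatment sequence and treatment period as fixed factors".

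Other sections bear on what is meant:

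- Section 2.1, primary objective: "Evaluate changes in convulsive and/or drop seizure frequency from Baseline following ataluren treatment".
- Section 2.2.1 lists five types to be counted: tonic-clonic, hemiclonic, atonic/drop, tonic and focal motor. Persistence or disappearance of myoclonic seizures appears under the same heading, but myoclonic seizures are not in the count.
- Section 2.2.2 makes the numbers of myoclonic, staring and other seizures secondary endpoints.
- Section 7.4.1 says the baseline total "is defined as the total number of seizures/emergency room visits/hospitalizations during the 4-week Screening Period". It fixes the time window and names no types.
- Section 7.7, descriptive tables: "Summary statistics for the total numbers of the following measurements per 28 days". Here the word total means the count of each listed item.

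**The concern.** The lead-in names one variable, and all three operational statements (d_ij, the rank-model outcome and its baseline covariate) name another. A programmer implements the operational statements. With the seizure types in the total left unstated, two analysts working from the same diaries could form different primary datasets and each cite 7.7 in support.

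What is at stake is the estimate and interval reported for the stated primary objective. An all-type count would mix the primary endpoint with seizures that the protocol assigns to a secondary endpoint. In a trial this small, that choice should not still be open when treatment codes are available.

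**Working it through.** **No figure to reproduce.** Section 7.1 says the study was not powered for testing, and 7.7 attaches no number to the primary variable. The check is therefore a comparison of the text, followed by the algebra that shows when the wording matters.

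**Step 1: the terms side by side.**

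| Place | Variable named | Types stated there? |
|---|---|---|
| 2.1, primary objective | convulsive and/or drop | no; listed in 2.2.1 |
| 2.2.1, primary endpoint | convulsive and/or drop | yes, five |
| 7.7, lead-in | convulsive | no; 2.2.1 applies naturally |
| 7.7, d_ij | total | no |
| 7.7, rank-model outcome | total | no |
| 7.7, rank-model covariate | baseline total | no |
| 7.4.1, baseline | total number of seizures | no |

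No section equates the total with the convulsive count. The clinically meaningful difference in 7.4.1, a "reduction in seizure frequency over placebo" of at least 20%, names no types either, so it does not settle the question.

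**Step 2: when the two variables agree.** For one child, let C and M be the baseline convulsive and minor counts per 28 days, and let s = C/(C + M). Let c and m be the percent changes from baseline in the two groups. Then

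percent change in all-type total = (C·c + M·m)/(C + M) = s·c + (1 − s)·m.

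Both periods use the same baseline, so the period differences combine in the same way: d_total = s·d_c + (1 − s)·d_m. Hence

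d_total − d_c = (1 − s)(d_m − d_c).

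This is zero only if s = 1 (no minor seizures) or d_m = d_c (equal change in both groups).

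**Step 3: direction, with assumed values only.** The documents give neither s nor an effect by seizure type. Take c = −20% as an assumption:

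- Minor seizures unchanged (m = 0): the all-type change is s × (−20%). That is −20% at s = 1.0, −15% at 0.75, −10% at 0.5, −5% at 0.25 and −2% at 0.1.
- Minor seizures also fall 20%: −20% at every s.
- Minor seizures rise 20%: at s = 0.5, 0.5(−20) + 0.5(20) = 0%; at s = 0.25, 0.25(−20) + 0.75(20) = +10%.

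**Step 4: ordering of children.** Assume two children, each with 20 convulsive and 50 minor seizures at baseline.

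- Child A: convulsive −50%, minor +30%. All-type change = (−10 + 15)/70 = +7.1%.
- Child B: convulsive −10%, minor −30%. All-type change = (−2 − 15)/70 = −24.3%.

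A has the larger fall on the convulsive count and B on the all-type total. The planned methods work on ranks and pairwise differences. A reordering that moves children relative to those in the other sequence can therefore change the test and the interval as well as the point estimate.

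**The case against.** The strongest reply is that the paragraph, read as a whole, is clear. The d_ij sentence opens as an abridgement of a method just assigned to the convulsive variable. In the descriptive tables of 7.7, total numbers means the count of each item, and in 7.4.1 total covers emergency room visits and hospitalizations as well as seizures. Both uses suggest a sum over a time window, not a sum over seizure types. No objective or endpoint names an all-seizure composite, and 2.2.1 does list the types for the primary count.

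Most of this stands, and it makes the convulsive reading the more natural one. A reader might infer from the formula that the primary analysis will pool minor seizures, or that the wrong variable has been chosen. The documents do not support that inference: they show an inconsistent term that would permit such an analysis, not a decision to carry it out.

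The reply does not remove the inconsistency. The paragraph on the supportive model never repeats the word convulsive, the 7.4.1 baseline is untyped, and no sentence says that total means total convulsive.

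**Conclusion.** The inconsistency is real and lies in the rule that defines the primary test, so it should be corrected before unmasking. Its numerical effect cannot be stated. It depends on each child's share of minor seizures and on how those seizures change, and the documents give neither. The figures in the working show direction only. A reader should not take any of them as the expected dilution of the trial's estimate, and the effect is nil if minor seizures are absent or change in proportion.

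The consequence is limited. Section 7.1 says the study was not powered for testing, no decision rule depends on the result, and convulsive/motor seizures are tabulated under either reading. The reason to act is that 7.1 expects an initial assessment of efficacy from these data, and that assessment should rest on one defined variable.

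**What to change.** Before unmasking:

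1. In 7.7, use a single term in the lead-in, in d_ij, in the rank-model outcome and in its baseline covariate: convulsive and/or drop seizure frequency per 28 days, being the sum of the five types in 2.2.1.
2. In 7.4.1, define the matching baseline as the count of those same types in the Screening Period, expressed per 28 days as 7.7 already implies.
3. If an all-type total is wanted, list its types and label it a separate secondary analysis.

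The cost is wording only, with no new data. The convulsive/drop baseline can be formed whether the Screening diary is as described in 3.3 (convulsive or drop seizures) or in 6.1.1.1 (seizure type recorded). An all-type baseline under item 3 is assured only by the description in 6.1.1.1, so that should be confirmed first.
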